## 5. Research Flow Process

The Flow Chart of this research will be completed in three stages and four steps as indicated in Figure 1.

**First Stage (Preparatory Stage):** An internationally approved acupressure certificate was obtained by the researcher in July 2022 (the certificate is in Annex I). The place where the acupressure application will be made will be arranged in accordance with the acupressure application. Necessary materials will be purchased for acupressure application (bed cover, pillow, etc.)

**Second Stage (Implementation Stage):** This stage will consist of four steps.

**In the first step:** In the first step of the application, patients who receive hemodialysis treatment in Adana City Hospital dialysis unit and meet the research criteria and are willing to participate in the research will be given brief information about the research and their verbal consent will be obtained. The fatigue experience VAS scores of the patients who accepted to participate in the study on a voluntary basis will be calculated. Those with a VAS value of fatigue severity  $\geq 4.0$  between 0 and 10 points will constitute the sample of the study.

**In the second step:** Sample selection will be completed in accordance with the inclusion, exclusion and exclusion criteria of the study, and then randomization will be performed. The patients will be informed about the purpose of the research and the research process, and the patients will be asked to fill in the "Piper Fatigue Scale", "Kidney Disease and Quality of Life Form" and "Hemodialysis Comfort Scale" as a pre-test with an informed consent form.

**Third step:** Patients in the study group will be given a total of 12 sessions of acupressure application bilaterally to Stomach 36 (St36), Gall Bladder 34 (GB34), Spleen 6 (SP6) and Kidney 1 (K1) acupuncture points for 4 weeks and 3 days a week for 20 minutes. No intervention will be made to the control group other than routine maintenance during the four-week period.

**Fourth step:** After the 4-week acupressure process is over, after the last acupressure session, the patients in the study group will have the "Piper Fatigue Scale", "Kidney Disease and Quality of Life Form" and "Hemodialysis Comfort Scale" filled face-to-face as a post-test. At the end of 4 weeks, the control group will have to fill in the "Piper Fatigue Scale", "Kidney Disease and Quality of Life Form" and "Hemodialysis Comfort Scale" as a post-test before hemodialysis.

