**Third Stage (Reporting Stage):** At this stage Statistical analysis of the data obtained from the patients will be made and a research report will be written.

**NCT Number:** 05892679

The Effect of Acupressure on Fatigue, Quality of Life and Comfort in Hemodialysis Patients. Randomized Controlled Study

**Figure 1.** Flow Chart of the Research

STAGE 1. PREPARATION STAGE	
Arrangement of Adana City Hospital dialysis unit in accordance with acupressure application in order to perform acupressure application.
		
STAGE 2 IMPLEMENTATION PHASE	1. Step	
Contacting patients receiving hemodialysis treatment in Adana City Hospital dialysis unit, Determining compliance with the criteria, Measuring fatigue experience VAS scores, Recruiting patients willing to participate in the study
	
	2. Step	
Determining the sample according to the criteria Performing the randomization (Study Group; n=30 - Control Group; n=30) Getting Informed Consent and pre-test data collection forms ("Patient Description Form", "Piper Fatigue Scale", "Kidney Disease and Quality of Life Form" and "Hemodialysis Comfort Scale")
	
	3. Step	
Making acupressure group (n=30) apply acupressure for 20 minutes three times a week for four weeks.
	
No intervention in the control group (n=30)

	4. Step	
Having the study group (n=30) fill out the post-test data collection forms ("Piper Fatigue Scale", "Kidney Disease and Quality of Life Form" and "Hemodialysis Comfort Scale") after the last acupressure session, after the 4-week acupressure process is over.
	
The control group to be fill out the post-test data collection forms ("Piper Fatigue Scale", "Kidney Disease and Quality of Life Form" and "Hemodialysis Comfort Scale") at the end of the interview at the end of 4 weeks.

STAGE 3 REPORTING PHASE	
ANALYSIS OF DATA AND WRITTEN RESEARCH REPORT
		

**NCT Number:** 05892679

The Effect of Acupressure on Fatigue, Quality of Life and Comfort in Hemodialysis Patients. Randomized Controlled Study

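### The post-test is placed relative to dialysis for the control group only, so the plan lets the two arms be assessed at different points of the dialysis day

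*Combined protocol and SAP*

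**What the plan says.** The fourth step of the Research Flow Process gives each arm its own post-test rule.

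- **Study group:** once the four-week course is over, "after the last acupressure session, the patients in the study group will have the" three scales "filled face-to-face as a post-test". Dialysis is not mentioned.
- **Control group:** "At the end of 4 weeks, the control group will have to fill in the" same scales "as a post-test before hemodialysis". The mode of completion is not mentioned.

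Figure 1, step 4, keeps the session anchor for the study group ("after the last acupressure session, after the 4-week acupressure process is over"). For controls it says "at the end of the interview at the end of 4 weeks" and does not repeat the dialysis condition. The outcome-timing sentence in section 4.3 refers to the fourth week and does not mention dialysis.

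The third step schedules the sessions "for 4 weeks and 3 days a week for 20 minutes", without placing them before, during or after dialysis. In the second step the scales are given "as a pre-test with an informed consent form", again with no dialysis position, in either arm.

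**The concern.** The primary outcome is self-reported fatigue in dialysis patients, and the rationale in section 3 itself attributes fatigue to hemodialysis. If ratings depend on whether a patient is about to start dialysis, is on it or has just finished, the time of asking becomes part of the measurement. The authors fixed that time for controls and left it open for the arm being compared with them.

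Randomization does not help, because a timing difference of this kind arises after assignment and follows it. Section 4.1 plans independent-samples t-tests at each measurement and a repeated-measures ANOVA. Neither contains anything that distinguishes a timing shift from an acupressure effect. The same would apply to quality of life and comfort if those scores also vary with the dialysis day, which the documents do not say.

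**Working it through.** **1. Timing statements side by side**

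| Place | Study group | Control group |
|---|---|---|
| Research Flow Process, fourth step | After the last session, end of the four-week course; dialysis position not stated | End of four weeks; before hemodialysis |
| Figure 1, step 4 | After the last session, end of the four-week course; dialysis position not stated | End of four weeks; dialysis position not stated |
| Section 4.3, outcome timing | Fourth week; dialysis position not stated | Same sentence |
| Third step, session schedule | 12 sessions of 20 minutes, three days a week; dialysis position not stated | No sessions |
| Second step, pre-test | Dialysis position not stated | Dialysis position not stated |

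The calendar time agrees. The dialysis position is given once, for controls. If the last session comes before dialysis, the two rules can describe the same slot. If it comes during or after dialysis, they cannot. Nothing in the documents decides between these cases.

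**2. The plan's own sample-size figure**

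This point does not depend on it, but it supplies the group sizes used below. With f = 0.5, two measurements and correlation 0.5, λ = f² × N × m / (1 + (m − 1)ρ) = 0.25 × 42 × 2 / 1.5 = 14.0. The critical F(1, 40) is 4.0847 and the power 0.9545, as printed in section 4.3. Allowing for 30% loss, 21 / 0.70 = 30 per group.

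**3. Illustration of what a shift would do**

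The documents give no shift, so b below is assumed. The setting is no true effect, a two-sided 5% independent-samples t-test at post-test, n per arm, df = 2n − 2, and noncentrality b × √(n/2). With n = 30, √15 = 3.873, so b = 0.2, 0.3 and 0.5 SD give noncentralities 0.775, 1.162 and 1.936.

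| False-positive rate | b = 0 | b = 0.2 | b = 0.3 | b = 0.5 |
|---|---|---|---|---|
| t-test, whole study arm shifted, 30 per arm | 0.050 | 0.119 | 0.208 | 0.478 |
| t-test, half the study arm (15 of 30) shifted, simulation of 100,000 trials per case | 0.050 | 0.066 | 0.087 | 0.151 |
| t-test, whole study arm shifted, 21 per arm | 0.050 | 0.097 | 0.158 | 0.353 |
| Between-factors repeated-measures test, whole arm shifted at post-test only, 30 per arm | 0.050 | 0.072 | 0.101 | 0.196 |

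For the last row, the test uses the mean of the two measurements. The shift is halved to b/2, and the SD of the mean is √((1 + 0.5)/2) = 0.866, so the standardized shift is 0.577b.

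A group-by-time test gets no such dilution. At correlation 0.5 and equal variances the change score has variance 2(1 − 0.5) = 1, the same as a single measurement, so a shift at post-test only gives the rates in the first row.

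**The case against.** The strongest reply is that this is an ambiguity and not a demonstrated difference. Controls have no last session, so some difference in wording is unavoidable, and sessions given before dialysis would make the two slots the same. The contrast also rests on a single phrase: Figure 1 drops the dialysis condition for controls, and section 4.3 does not mention dialysis for anyone. No passage says that scores on the three scales change within the dialysis day. The numerical illustration is sensitive to its inputs, since 21 per arm or the between-factors test gives clearly lower rates, and the highest figure needs a 0.5 SD shift in every study patient with no attrition.

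Much of this is right and limits the claim. It is confined to the text available for review. The size and direction of any bias are unknown, and its existence is not shown. The face-to-face wording is not evidence that mode differs, because the interview mentioned for controls in Figure 1 may mean the same thing. The missing pre-test position affects both arms alike.

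The specification gap remains. The plan states arm-specific rules for the primary outcome, and a common dialysis position could be stated even though only one arm has sessions. The omission in Figure 1 is a further inconsistency to resolve; it does not make the rules agree.

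**Conclusion.** The point holds. As written, the plan fixes the post-test relative to dialysis for controls and leaves it open for the study group, which permits a timing difference that tracks treatment and that the planned analyses cannot remove.

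How much this matters cannot be derived from the documents. Under the assumed shifts, the post-test t-test's false-positive rate with 30 per arm runs from 5% (slots coincide) to 48% (whole arm shifted by 0.5 SD), with 7% to 15% if only half the arm is affected. These figures rest on assumed shifts, an assumed affected fraction and no true effect; they show sensitivity and are not estimates of bias. This should be fixed, with moderate confidence that it would matter in practice.

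**What to change.** Reconcile the fourth step, Figure 1 and the timing sentence in section 4.3 into one assessment rule for both arms:

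- the same point relative to dialysis at post-test, for example before hemodialysis, as the fourth step already has it for controls;
- the same face-to-face mode in both arms;
- the same rule at pre-test;
- the interval between the last acupressure session and the study-arm post-test, stated explicitly.

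If the data have already been collected, report the actual timing relative to dialysis and the mode by arm, and limit the conclusions accordingly.

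The cost is wording in three places. With the example slot, some study-arm forms may move to the next routine dialysis visit, slightly beyond the fourth week named in section 4.3 and further from the last session. That is a real trade-off, and it is why the interval needs to be stated. The change concerns only when and how questionnaires are completed.

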## 5. Data Collection Tools of the Research

“Data Collection Form” will be used in the data collection phase of the research.

### 5.1. Data Collection Form

In the study, data will be collected with a data collection form consisting of four parts: "Patient Description Form", "Piper Fatigue Scale", "Kidney Disease and Quality of Life Form (KDQOLTM-36)" and "Hemodialysis Comfort Scale".

